## 9.1.2 Grading and Relationship to Drug

The descriptions and grading scales found in the CTEP Version 4 of the NCI Common Terminology Criteria for Adverse Events (CTCAE) will be utilized for AE reporting. CTEP Version 4 of the CTCAE is identified and located at: [http://ctep.cancer.gov/protocolDevelopment/electronic\\_applications/ctc.htm](http://ctep.cancer.gov/protocolDevelopment/electronic_applications/ctc.htm).

AEs not covered by specific terminology listed should be reported with common medical terminology, and documented according to the grading scales provided in the CTCAE Version 4.

The relationship of event to study drug will be documented by the Investigator as follows:

- **Unrelated:** The event is clearly related to other factors such as the subject’s clinical state, other therapeutic interventions or concomitant drugs administered to the patient.
- **Unlikely:** The event is doubtfully related to investigational agent(s). The event was most likely related to other factors such as the patient’s clinical state, other therapeutic interventions, or concomitant drugs.

- **Possible:** The event follows a reasonable temporal sequence from the time of drug administration, but could have been produced by other factors such as the patient's clinical state, other therapeutic interventions or concomitant drugs.
- **Probable:** The event follows a reasonable temporal sequence from the time of drug administration, and follows a known response pattern to the study drug. The event cannot be reasonably explained by other factors such as the patient's clinical state, therapeutic interventions or concomitant drugs.
- **Definite:** The event follows a reasonable temporal sequence from the time of drug administration, follows a known response pattern to the study drug, cannot be reasonably explained by other factors such as the patient's condition, therapeutic interventions or concomitant drugs; AND occurs immediately following study drug administration, improves upon stopping the drug, or reappears on re-exposure.

### 9.1.3 Reporting Adverse Events (Network Sites see Appendix A )

**Table 7. Guidelines for Routine Adverse Event Reporting for Phase 1 Studies (Regardless of Expectedness)**

Attribution	Grade 1	Grade 2	Grade 3	Grade 4
Unrelated	X	X	X	X
Unlikely	X	X	X	X
Possible	X	X	X	X
Probable	X	X	X	X
Definite	X	X	X	X

**Table 8. Guidelines for Routine Adverse Event Reporting for Phase 2 Studies (Regardless of Expectedness)**

Attribution	Grade 1	Grade 2	Grade 3	Grade 4
Unrelated			X	X
Unlikely			X	X
Possible	X	X	X	X
Probable	X	X	X	X
Definite	X	X	X	X

Routine AEs occurring between the start date of intervention until 30 days after the last intervention or until the event has resolved, the study patient is lost to follow up, the start of a new treatment, or until the study investigator assesses the event(s) as stable or irreversible, will be reported. New information will be reported after it is received.

## **9.2 Serious Adverse Events**

### **9.2.1 Definition**

A serious adverse event (SAE) is any adverse event (experience) that in the opinion of either the investigator or sponsor results in **ANY** of the following:

- Death.
- A life-threatening adverse event (experience). Any AE that places a patient or patients, in the view of the Investigator or sponsor, at immediate risk of death from the reaction as it occurred. It does **NOT** include an AE that, had it occurred in a more severe form, might have caused death.
- Inpatient hospitalization or prolongation of existing hospitalization (for > 24 hours).
- A persistent or significant incapacity or substantial disruption of the ability to conduct normal life functions.
- A congenital anomaly or birth defect.
- Important Medical Event (IME) that, based upon medical judgment, may jeopardize the patient or patient and may require medical or surgical intervention to prevent one of the outcomes listed above.

### **9.2.2 Reporting Serious Adverse Events (Network Sites see Appendix A )**

All new SAEs occurring from the date the patient signs the study consent until 30 days after the last intervention or a new treatment is started, whichever comes first, will be reported.

The RPCI SAE Source Form is to be completed with all available information, including a brief narrative describing the SAE and any other relevant information.

SAEs occurring after the 30 day follow-up period that the investigator determines to be possibly, probably or definitely related to the study intervention should be reported.

SAEs identified as an Unanticipated Problem by the Investigator must be reported. Please refer to Section 9.3.2 for details on reporting Unanticipated Problems.

### **9.2.3 Follow-Up for Serious Adverse Events**

All related SAEs should be followed to their resolution, until the study patient is lost to follow up, the start of a new treatment, or until the study investigator assesses the event(s) as stable or irreversible. New information will be reported when it is received.

### 9.3 Unanticipated Problems

#### 9.3.1 Definition

An Unanticipated Problem (UP) is any incident, experience, or outcome that meets all of the following criteria:

- Unexpected (in terms of nature, severity, or frequency) given:
  - The research procedures that are described in the study-related documents, including study deviations, as well as issues related to compromise of patient privacy or confidentiality of data.
  - The characteristics of the patient population being studied.
- Related or possibly related to participation in the research (possibly related means there is a reasonable possibility that the incident, experience, or outcome may have been caused by the procedures involved in the research).
- Suggests that the research places patients or others at a greater risk of harm (including physical, psychological, economic, or social harm) than was previously known or recognized and if in relation to an AE is also deemed **Serious** per **Section 9.2**.

#### 9.3.2 Reporting Unanticipated Problems

Unanticipated problem reporting will begin at the time of participant consent. An Unanticipated Problem shall be submitted to the CRS Compliance Office as “Reportable New Information” in the Click system within 1 business day of becoming aware of the Unanticipated Problem. After review, CRS Compliance will submit the UP to the IRB.

When becoming aware of new information about an Unanticipated Problem, submit the updated information to CRS Compliance as “Reportable New Information” in the Click system.

**Network Sites, see Appendix (A) for information regarding, Unanticipated Problem reporting.**

### 9.4 Investigator Reporting: Notifying the Study Sponsor

Adverse events, both serious and non-serious, and deaths that occur during the patient’s study participation (from time of the first dose of tivozanib, written informed consent through 30 days after receiving the last dose of tivozanib hydrochloride) will be documented. All subjects receiving at least 1 dose of tivozanib hydrochloride, whether completing the treatment period or not, should be followed for 30 days after the last dose of tivozanib hydrochloride. New AEs and changes in ongoing AEs or those with an unknown outcome must be followed for 30 days after the last dose of tivozanib hydrochloride. All SAEs should be monitored until they are resolved or are clearly determined to be due to a patient’s stable or chronic condition or intercurrent illness(es). The Investigator will determine the seriousness, intensity, and causality of an adverse

event associated with the use of the study drug (i.e., events where there is a reasonable possibility that the event may have been caused by the study drug).

All SAEs should be recorded on a Medwatch Form 3500A and sent to the FDA (if applicable), to AVEO Pharmacovigilance/Drug Safety, to the NCCN, and to the Principal Investigator/ CRS Network Coordinators at [contact].

SAE Reporting Contact Information: please submit SAE Reports to Parexel GPPG via email ([contact]). If submission via email is not possible or delayed then submission via fax (NA [contact]) is acceptable.

Pharmacovigilance/Drug Safety  
AVEO Pharmaceuticals, Inc  
[name]  
[name]  
[contact]  
E-mail: [contact]

SAE Reporting Contact Information  
National Comprehensive Cancer Network (NCCN)  
[contact]

## 9.5 FDA Reporting

This protocol is being conducted under a RPCI, IND and it is the responsibility of the study IND holder to report certain AEs or Unanticipated Problems to the FDA.

RPCI's Compliance Office will report Network Site reports to the FDA.

The following describes the FDA reporting requirements by timeline for AEs and new safety findings that meet the criteria outlined below:

### Within 7 Calendar Days

Any adverse event that meets **ALL** the following criteria:

- Related or possibly related to the use of the study drug;
- Unexpected; and
- Fatal or life-threatening.

### Within 15 Calendar Days

Any adverse event that meets **ALL** the following criteria:

- Related or possibly related to the use of the study drug;
- Unexpected; and
- Serious but not fatal or life-threatening.

Or meets **ANY** of the following criteria:

- A previous adverse event that is not initially deemed reportable but is later found to fit the criteria for reporting (report within 15 days from when event was deemed reportable).
- Any findings from other studies, including epidemiological studies, pooled analysis of multiple studies, or other clinical studies conducted with the study drug that suggest a significant risk in humans exposed to the drug.
- Any findings from animal or in vitro testing that suggest a significant risk for human subjects including reports of mutagenicity, teratogenicity, or carcinogenicity or reports of significant organ toxicity at or near the expected human exposure.
- Any clinically important increase in the rate of occurrence of a serious, related or possibly related adverse event over that listed in the protocol or investigator brochure.

Sponsors are also required to identify in IND safety reports, all previous reports concerning similar adverse events and to analyze the significance of the current event in the light of the previous reports.

### **Reporting Process**

The principal investigator or designee will complete and submit a FDA Form 3500A for any event that meets the above criteria. Forms will be submitted to the CRS Compliance Office via email: [[contact]](mailto:[contact]). The Compliance office will send the form to the Administrator of ORSP.

### **9.6 Procedures for Reporting Subject Death**

Any death experienced by a subject after enrollment through 30 days of receiving the last dose of tivozanib hydrochloride, regardless of relationship to study drug, or any death that occurs more than 30 days after receiving study drug that is believed to be study drug-related must be promptly reported (within 24 hours of the investigator becoming aware of the event) by telephone, telefax, or e-mail transmission to AVEO Pharmacovigilance/Drug Safety. Reports of all on-study deaths must also be communicated promptly to the FDA (if applicable) and the appropriate Institutional Review Board (IRB) and/or reported in accordance with local law and regulations.

### **9.7 Procedures for Reporting Study Drug Overdose**

An overdose of tivozanib hydrochloride should be reported if the dose of tivozanib hydrochloride administered is greater than the assigned dose for the subject.

Should a subject experience an overdose during the course of the study (whether symptomatic or not, and regardless of seriousness), the Sponsor-Investigator or qualified designee must complete a Medwatch Form 3500A to report the overdose to AVEO Pharmacovigilance/Drug Safety within 24 hours of first becoming aware of the overdose. Follow-up information on the outcome of the overdose should be forwarded to the AVEO Pharmacovigilance/Drug Safety.

Any event associated with, or observed in conjunction with, a product overdose (whether accidental or intentional) or a product abuse and/or withdrawal is considered an AE and should

be reported as such. If a SAE occurs in conjunction with the overdose, then the reporting time frame for a SAE should be followed.

### **9.8 Procedures for Reporting Drug Exposure During Pregnancy and Birth Events**

All pregnancies, including pregnancies in female partners of male study participants, occurring from the date of ICF signature until 45 days following tivozanib hydrochloride administration must be documented. If it is confirmed that a study participant has become pregnant while participating in this trial, study drug administration will be discontinued immediately. Any pregnancy occurring during this study will be reported immediately to AVEO Pharmacovigilance/Drug Safety.

The Sponsor-Investigator must actively follow-up, document and report the outcome of any pregnancy even if the subject has withdrawn from the study. The Sponsor-Investigator will then report follow-up information to AVEO Pharmacovigilance/Drug Safety regarding the course of the pregnancy, including perinatal and neonatal outcome. Timelines vary according to the nature of the pregnancy outcome:

- For normal outcomes, AVEO Pharmacovigilance/Drug Safety should be notified within 45 days from birth/delivery.
- For abnormal outcomes, the fully completed Medwatch Form 3500A must be sent to AVEO Pharmacovigilance/Drug Safety according to the same procedures and timelines described for expedited AE reporting.

For questions related to safety reporting, contact: AVEO Pharmacovigilance/Drug Safety.

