**Title: Multicenter Phase 1b/ 2 Study of Tivozanib in Patients with Advanced Inoperable Hepatocellular Carcinoma**

INCLUSION CRITERIA				
Yes	No	N/A	All answers must be "YES" or "N/A" for subject enrollment.	DATE
			6. Patients must not have any evidence of bleeding diathesis or active gastrointestinal bleeding.	
			7. Patients must not be known to be HIV positive; drug-drug interaction with study medication and HIV medications is not well-characterized and could lead to unwanted side effects.	
			8. Patients must not have other uncontrolled intercurrent illnesses (excluding HBV or HCV). This includes (but is not limited to) ongoing or active infection, symptomatic congestive heart failure, unstable angina pectoris, cardiac arrhythmia, or psychiatric illness/social situations that would limit compliance with study requirements.	
			9. Sexually active fertile patients (male and female), and their partners, must agree to use medically accepted methods of contraception during the course of the study and for 3 months after the last dose of the study drug.	
			10. Female patients of childbearing potential must have a negative pregnancy test at screening.	
			11. Have an ECOG Performance Status of $\leq 2$ . Refer to Appendix B .	
			12. Subject or legal representative must understand the investigational nature of this study and sign an Independent Ethics Committee/Institutional Review Board approved written informed consent form prior to receiving any study related procedure.	

**Investigator Signature:** \_\_\_\_\_

**Date:** \_\_\_\_\_

Roswell Park Cancer Institute Study No.: I 229112

**Subject Name: (Network Sites use Subject Initials)** \_\_\_\_\_

**Medical Record No.: (Network Sites use Subject ID#)** \_\_\_\_\_

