9. Sexually active fertile patients (male and female), and their partners, must agree to use medically accepted methods of contraception during the course of the study and for 3 months after the last dose of the study drug.
10. Female patients of childbearing potential must have a negative pregnancy test at screening.
11. Have an ECOG Performance Status of  $\leq 2$ . Refer to **Appendix B**.
12. Subject or legal representative must understand the investigational nature of this study and sign an Independent Ethics Committee/Institutional Review Board approved written informed consent form prior to receiving any study related procedure.

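### The only dated pregnancy documentation rule stops 45 days after tivozanib, about halfway through the 3-month contraception period, and it is unclear whether later pregnancies must be reported

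*Combined protocol and SAP*

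**What the plan says.** **Contraception.** Section 4.1, item 9, covers sexually active fertile patients of both sexes and their partners, who have to use recognised "methods of contraception during the course of the study and for 3 months after the last dose of the study drug". Item 9 of the eligibility checklist gives the same period: "for 3 months after the last dose of the study drug".

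**Pregnancy documentation.** Section 9.8 covers "All pregnancies, including pregnancies in female partners of male study participants", and requires that those "occurring from the date of ICF signature until 45 days following tivozanib hydrochloride administration must be documented". The 45 days are counted from administration of tivozanib; the words 'last dose', which item 9 uses, do not appear in this clause.

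**Pregnancy reporting and follow-up.** Two more sentences in section 9.8 have no day limit. One reads "Any pregnancy occurring during this study will be reported immediately to AVEO Pharmacovigilance/Drug Safety". The other says that the Sponsor-Investigator "must actively follow-up, document and report the outcome of any pregnancy even if the subject has withdrawn from the study".

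**General safety capture.** Section 9.4 says that treated subjects "should be followed for 30 days after the last dose of tivozanib hydrochloride". Section 9.2.2 extends reporting past 30 days only for serious events judged possibly, probably or definitely related. Section 9.2.1 lists congenital anomaly or birth defect as a seriousness criterion. After treatment ends, section 7.8 and the notes to Table 4 provide for a record review every 6 months, for overall survival.

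**The concern.** The protocol asks patients to avoid pregnancy for 3 months after the last dose but requires pregnancies to be documented for only 45 days. Nothing in it extends the shorter period or explains why the two differ. A site that follows the dated sentence of section 9.8 as written could leave a pregnancy in the second half of the contraception period undocumented and still consider itself compliant. Another site, relying on the undated sentences of the same section, could report the same pregnancy. In a multicenter trial that means uneven capture of the exposures and perinatal outcomes that section 9.8 exists to collect. A pregnancy missed at the time may not be recoverable later.

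**Working it through.** The plan gives no derived figure to reproduce; both periods are stated outright. The check is their difference, followed by a search for any other rule that covers the remainder.

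**Inputs**
- Contraception after the last dose: 3 months (section 4.1 item 9; checklist item 9). This is 89 to 92 days depending on the calendar months, and 84 days if read as 12 weeks.
- Pregnancy documentation after dosing: 45 days (section 9.8). Assumption: counted from the last dose.

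**Formula**

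Uncovered days = C − 45; uncovered share = (C − 45) / C, where C is the contraception period in days.

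| C (days) | Uncovered days | Uncovered share |
|---|---|---|
| 84 | 84 − 45 = 39 | 39/84 = 46.4% |
| 89 | 89 − 45 = 44 | 44/89 = 49.4% |
| 90 | 90 − 45 = 45 | 45/90 = 50.0% |
| 92 | 92 − 45 = 47 | 47/92 = 51.1% |

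The share is about half for any calendar reading of 3 months, and a little under half even at 12 weeks.

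**Does another rule cover day 46 to month 3?**

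1. *Immediate reporting (section 9.8).* Limited to pregnancies during the study, with no definition of when the study ends for a patient. It could mean while on treatment, until 30 days after the last dose, or through survival follow-up. Only the last of these reaches month 3.
2. *Outcome follow-up (section 9.8).* Applies to any pregnancy, including after withdrawal. It governs what is done once a pregnancy is known and sets no period in which pregnancies are to be sought or notified.
3. *Adverse event rules (sections 9.2.2 and 9.4).* New events are collected to 30 days, which ends before the 45 days do. Beyond that, only serious events judged related are reportable. A related congenital anomaly would qualify; an uncomplicated pregnancy, or an outcome judged unrelated, would not.
4. *Scheduled contact (sections 7.1 and 7.8, Table 4).* The only pregnancy test is at baseline. The later 6-monthly review is of medical records, for survival, and cannot be relied on to show a partner's pregnancy.

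None of these clearly requires every pregnancy from day 46 to month 3 to be documented, and none rules out its being reported.

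**The case against.** The strongest reply is that section 9.8 is wider than its dated sentence. The 45-day limit attaches to documentation only. Immediate reporting and outcome follow-up are not so limited, and the latter explicitly survives withdrawal. Section 3.4 puts time on study at about 2 years and survival follow-up continues after treatment, so a broad reading would take in days 46 to 90. Related birth defects stay reportable as late serious events, and section 9.3.2 starts unanticipated-problem reporting at consent with no stated end. This stands in part. A reader might infer that pregnancies in months 2 and 3 go unrecorded, or that their outcomes would not be followed. The documents do not support that; they leave it open. The broad reading does not settle the matter either, because it leaves the 45-day limit with little purpose.

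It can also be said that a contraception undertaking and a documentation rule are different things, that both can be obeyed at once, and that a contraception period may include a margin. That is fair. This is a mismatch without explanation, not a strict contradiction. Nor do the documents call the 3 months a period of risk or hazard: item 9 gives no reason for its length, and that label would be inferred from the contraception rule alone.

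Finally, half of the calendar days is not half of the exposed pregnancies. That stands too.

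**Conclusion.** The point holds as a low-severity reconciliation. The only dated pregnancy documentation rule ends 45 days after tivozanib, while contraception is required for 3 months after the last dose. About 44 to 47 days, roughly half of the contraception period, fall outside mandatory documentation, and section 9.8 is ambiguous on whether pregnancies in that interval must be reported.

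The size rests on two assumptions: that the 45 days run from the last dose, and that 3 months means 89 to 92 days. The number of pregnancies involved cannot be estimated from the documents. It is expected to be small in a trial of at most 49 patients (section 3.4). The primary endpoint, sample size and error rates do not change. The documents do not show which of the two periods is the intended one. The consent pages were not available, so they may already ask patients to report later pregnancies.

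**What to change.** Reconcile section 4.1 item 9, the matching checklist item and section 9.8 so that:

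- the pregnancy window in section 9.8 is counted from the last dose;
- it is no shorter than the contraception period the protocol requires (3 months if inclusion 9 stands);
- the same window governs documentation, immediate reporting to the supplier's drug safety unit, and identification of pregnancies for outcome follow-up;
- it applies equally to participants and to female partners of male participants.

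Section 9.8 could say, for example, that any pregnancy in a participant or partner, from consent until the end of the inclusion 9 contraception period after the last dose, is documented, reported immediately and followed to its outcome. If the two periods are meant to differ, the section should say so and explain why. The consent text should be checked for agreement.

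With inclusion 9 unchanged, the window lengthens by 44 to 47 days and the uncovered share falls from 49–51% to zero. The cost is an edit to one section, plus consent wording if needed, and minor follow-up work when a late pregnancy is reported. No visit or test is added. In turn, the change creates no new means of detection: capture still depends on patients telling the site.
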